**NCT04214080**

**23.03.2018**

## STUDY PROTOCOL

Scientific Background:	Trunk control of children with CP has been affected by spasticity, weakness in the trunk muscles, incoordination activation of trunk extensor and flexor muscles. Trunk stabilization exercises are an essential component of the mobility of distal part of body, including neck movements. Strengthening the deep neck flexor muscles and bridge exercise improves trunk control in children with CP. The positive effects of neck and trunk stabilization exercises on static and dynamic trunk balance, on upper limb and visuoperceptual function in CP have been mentioned in the literature.
Objectives:	According to literature there was a relationship between vocal functions and posture, active trunk movements has an important role in sound production and lastly trunk stabilization, balance and activity level components are in relationship with each other. Thus in this study, it was aimed to investigate the effects of neck and trunk stabilization exercises on communication, activities of daily living and quality of life in children with CP with oral motor problem.
Design:	The effects of structured neck and trunk stabilization exercises program giving together with feeding and oral-motor intervention strategies in children with Cerebral Palsy with oral motor problem: a randomized, single-blind, placebo controlled study. In this study, children were divided into study and control groups using a randomized numbers table. Structured oral motor rehabilitation and Neurodevelopmental therapy method-Bobath concept (NDT-B) approach was performed to all of the children who were in accordance with the inclusion criteria and approved by their families. In addition to the structured oral motor rehabilitation and NDT-B approach, Study group was received intensive structured neck and trunk stabilization exercises based on NDT-B principles.

Sponsor:	Marmara University, Istanbul, Turkey
Measured Parameters:	
 
-Gross motor functions,
 
-Daily communication performance,
 
-Speech production,
 
-The capacity to do the activities in daily life,
 
-The physical functions, psychosocial functions and school functionality independent of disease in children,
 
-Evaluation of trunk in sitting position.
 

Study Center:	Marmara University Pendik Education And Research Hospital, Istanbul, Turkey

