**“Evaluation of The Effect of Neck and Trunk Stabilization Exercises on
Quality of Life and Communication in Children with Cerebral Palsy with
Oral Motor Problem”**

NCT04214080

03.12.2019

Statistical Analysis Plan

Descriptive statistics for continuous variables are expressed as mean (X), standard deviation (SD) values (Height, weight, body mass index (BMI), gender, etc); it is expressed as number (n) and percentage (%) for categorical variables.

In calculations, statistical significance level (α) was taken as 5% and values with $p < 0.05$ expressed statistical significance. "Statistical Package for Social Sciences" (SPSS 16) statistics program was used for calculations.

Non-parametric tests were applied since the continuous variables in the study were not normally distributed. Mann-Whitney U test was used to compare continuous variables according to Control and Study groups (Visual Analogue Scale, Viking Speech Scale, Communication Function Classification System, Katz scale, Sub-parameters of PedsQL). Wilcoxon test was used for intra groups comparisons (Visual Analogue Scale, Viking Speech Scale, Katz scale, Sub-parameters of PedsQL). In determining the relationship between categorical variables and groups, Chi-square test was performed (CP subtypes, Number of Medication, Types of Medications).

Spearman's Correlation Analysis was used to determine the relationship between groups of cases and other categorical and continuous variables (Visual Analogue Scale and Katz scale correlation analysis results with Communication Function Classification Systems).

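### The groups are compared on VAS, Viking, Katz and PedsQL only by an unadjusted Mann-Whitney test of an unnamed score, although the SAP's own paired tests imply that baseline values exist

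*SAP*

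**What the plan says.** The third paragraph of the SAP gives the group comparison: "Mann-Whitney U test was used to compare continuous variables according to Control and Study groups". The scales listed for it are "Visual Analogue Scale, Viking Speech Scale, Communication Function Classification System, Katz scale, Sub-parameters of PedsQL". No covariate, score type or time point is attached.

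The next sentence covers change within each group: "Wilcoxon test was used for intra groups comparisons (Visual Analogue Scale, Viking Speech Scale, Katz scale, Sub-parameters of PedsQL". This list has the same scales except CFCS. The remaining tests are chi-square (CP subtypes and medication) and Spearman correlation, and neither adjusts a group comparison for baseline.

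The reason given for rank methods is "Non-parametric tests were applied since the continuous variables in the study were not normally distributed". Significance is set at 5%, with sidedness not stated.

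The Design entry of the protocol says that "children were divided into study and control groups using a randomized numbers table". It mentions no balancing on baseline scores. The protocol gives no assessment schedule and no analysis detail that would settle which score is tested.

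**The concern.** The between-group comparison is the one that answers the randomised question, and the SAP leaves open what is compared. A Wilcoxon paired test needs two values per child, so a baseline value for VAS, Viking, Katz and PedsQL appears to be in hand. A Mann-Whitney test of post-treatment scores ignores it. A test of change scores uses it only in part, unless the slope of post on baseline is 1. A test of baseline scores would be a comparability check and would not address the treatment effect at all.

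Two things are at stake. The first is precision: the same children could yield a sharper comparison. The second is chance imbalance: a single trial that happens to start with unequal groups can have its result moved by that inequality. While the score is unnamed, a reader also cannot tell which analysis was fixed in advance.

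**Working it through.** **Inputs.** From the SAP: Mann-Whitney with no covariate, paired tests on four instruments, alpha 5%. From the protocol: two randomised groups. The documents give no sample size, power, effect, SD or correlation, so there is no stated figure to reproduce and everything below is assumed. Tests are taken as two-sided; rho is the correlation between baseline and post-treatment scores.

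**Step 1, why the score matters.** For normal data with equal variances, relative to a post-score comparison (variance 1), a change score has variance 2(1 − rho) and a baseline-adjusted score 1 − rho².
- rho 0.5: 2 × 0.5 = 1.00 and 1 − 0.25 = 0.75
- rho 0.7: 2 × 0.3 = 0.60 and 1 − 0.49 = 0.51
- rho 0.85: 2 × 0.15 = 0.30 and 1 − 0.7225 = 0.2775

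Adjustment always beats post scores here, but its edge over change scores shrinks as rho rises.

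**Step 2, power by simulation.** 20,000 trials per setting, 20 per arm, 0.6 SD effect. The Mann-Whitney test is asymptotic and tie-corrected. Rank ANCOVA regresses ranked post score on group and ranked baseline, with a t-test on N − 3 df. Ceiling is at +0.5 SD; the four levels are cut at −0.674, 0 and 0.674. Entries are % power; the last two columns are differences in points.

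| Shape | rho | MW post | MW change | Rank ANCOVA | vs post | vs change |
|---|---|---|---|---|---|---|
| Normal | 0.5 | 43.5 | 43.4 | 52.8 | +9.3 | +9.4 |
| Normal | 0.7 | 43.7 | 64.3 | 67.6 | +23.9 | +3.3 |
| Normal | 0.85 | 43.5 | 90.7 | 88.3 | +44.8 | −2.4 |
| Ceiling | 0.5 | 40.1 | 29.6 | 47.2 | +7.1 | +17.6 |
| Ceiling | 0.7 | 38.7 | 41.5 | 57.5 | +18.8 | +16.0 |
| Ceiling | 0.85 | 39.9 | 63.3 | 77.7 | +37.8 | +14.4 |
| 4-level | 0.5 | 40.0 | 33.1 | 45.8 | +5.8 | +12.7 |
| 4-level | 0.7 | 40.0 | 46.0 | 56.7 | +16.7 | +10.7 |
| 4-level | 0.85 | 39.6 | 65.8 | 74.3 | +34.7 | +8.5 |

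Type I error over 60 null settings was 4.6–5.4% (post), 4.6–5.3% (change) and 4.7–5.4% (rank ANCOVA).

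**Step 3, vary the assumptions.**
- Effect size, 20 per arm, rho 0.5 to 0.85: the gain over post scores is about 2 to 21 points at 0.3 SD and 7 to 21 at 1.0 SD. The 45 is reached at 0.6 SD, 20 per arm and rho 0.85.
- Low correlation: the gain over post scores is 2 to 3 points at rho 0.3. At rho 0 there is a loss of 0.3 to 0.8.
- Small arms, normal data, 0.6 SD, rho 0.85, rank ANCOVA against change scores: at 15 per arm, 75.6 − 80.3 = −4.7; at 10 per arm, 54.4 − 63.0 = −8.6.
- Ceiling shape at 1.0 SD: rank ANCOVA is up to about 31 points ahead of change scores.
- A separate four-level model in which most children stay put and some gain one level: change and rank ANCOVA are nearly equal (66.8 vs 68.1%, 58.0 vs 59.6%, 46.1 vs 46.6%). Both are far above post scores (13.4, 13.6, 9.7%). This model lies outside the 0 to 45 range quoted for the three shapes above.

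**Step 4, chance imbalance.** With 20 per arm the SE of a baseline difference is √(2/20) = 0.316 SD. A difference above 0.5 SD is then 0.5/0.316 = 1.58 SE, which occurs in about 11% of trials (11.3% simulated). Among those null trials (rho 0.7, normal), false positives were 21.4% for post scores, 9.4% for change and 5.3% for rank ANCOVA. This is already contained in the overall 5%.

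**Step 5, what the rank ANCOVA estimates.** The difference in mean ranks equals N × (P(higher) + ½P(tie) − 0.5), so 0.5 + coefficient/N estimates P(higher) + ½P(tie). In the 4-level case this is 0.524 + 0.250/2 = 0.649, and the simulated mean was 0.649–0.651. Calling it a plain probability of scoring higher would be wrong where ties are common.

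**The case against.** The strongest reply is that two matters are joined here. The unnamed score is a reporting gap on the face of the SAP. The missing adjustment is a question of efficiency in a valid test, and its size depends on the gap. If change scores were tested, baseline is already partly used, and rank ANCOVA can be the weaker test when data are roughly normal, correlation is very high and arms are small. The large gains apply only to post scores. All of this stands, and it is why the size is given as a range.

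It also stands that the Wilcoxon pairs are baseline and post-treatment only by inference, since no time points are given. It remains the natural reading.

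The reply does not dispose of the point. Naming the score would settle the ambiguity but would still leave the randomised comparison without the baseline that the trial appears to hold.

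A reader might go further and infer that the Mann-Whitney test is biased or inflates false positives. It does not: randomisation protects it, and overall type I error stays near 5%. A reader might also infer from the SAP's past tense, and its date 620 days after the protocol's (23.03.2018 to 03.12.2019), that the score was chosen to suit the results. The documents suggest that data had been inspected. They do not show that any choice was driven by results.

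**Conclusion.** The point holds as one of precision and clarity. For VAS, Viking, Katz and the PedsQL sub-parameters, the only group comparison is an unadjusted rank test of a score that the SAP does not identify. CFCS is outside the point, because no paired test is listed for it.

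The loss in this trial cannot be computed. Under the assumptions of 10 to 20 per arm, effects of 0.3 to 1.0 SD, rho of 0.5 to 0.85, and normal, ceiling or four-level shapes, rank ANCOVA gains about 0 to 45 points over Mann-Whitney on post scores. Against Mann-Whitney on change scores it ranges from about 31 better (ceiling, 1.0 SD) to about 9 worse (normal, 10 per arm, rho 0.85). It would be tempting to say that this trial gave up 45 points of power. The documents support neither that figure nor the premise that post scores were tested.

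The change is worth making but not critical. Confidence is medium.

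**What to change.** 1. State for each scale which score the Mann-Whitney test compares (baseline, post-treatment or change) and at what time point.
2. For VAS, Viking, Katz and each PedsQL sub-parameter, add a rank ANCOVA: mid-rank post-treatment and baseline scores over both arms together, then regress ranked post on group (Control 0, Study 1) and ranked baseline.
3. Report 0.5 + (group coefficient / total N) with its 95% CI. Describe it as the baseline-adjusted probability that a Study child scores higher than a Control child plus half the probability of a tie. Say for each scale whether higher is better.
4. By default, keep Mann-Whitney as the stated analysis and label the rank ANCOVA post hoc and supportive, because the SAP already reports on the distribution of the variables. Make the rank ANCOVA the main comparison only if outcomes are still unseen; Mann-Whitney then becomes the sensitivity analysis.
5. Extend this to CFCS only if a baseline was recorded.

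**Cost.** SAP wording and a re-run on data that the paired tests imply are already collected, with no added children or visits. The effect scale is less familiar, and CI coverage can fall slightly below 95% (93.6–94.6%) at very high correlation. If baseline is uncorrelated with outcome, up to about 1 point of power is lost against post scores. Against change scores, with continuous data without a ceiling and very high correlation, the loss is about 2–3 points at 20 per arm, 5 at 15 and 8–9 at 10.

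### CP subtype is tested between the randomised arms by chi-square, which cannot show balance, while the outcome comparison makes no use of it; the cost is mainly lost precision

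*SAP*

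**What the plan says.** On allocation, the Protocol's Design entry says only that "children were divided into study and control groups using a randomized numbers table". It mentions no stratification, blocking or minimisation, and no allocation ratio.

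On subtype and medication, the SAP says: "In determining the relationship between categorical variables and groups, Chi-square test was performed (CP subtypes, Number of Medication, Types of Medications". The only criterion it gives is the general one: "statistical significance level (α) was taken as 5" per cent. It attaches no action to the result of these tests.

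On outcomes, the SAP says "Mann-Whitney U test was used to compare continuous variables according to Control and Study groups", and for changes within an arm "Wilcoxon test was used for intra groups comparisons". The one remaining analysis is a correlation: "Spearman's Correlation Analysis was used to determine the relationship between groups of cases and other categorical and continuous variables". None of these is a treatment comparison that is stratified by, or adjusted for, subtype, medication or baseline score. The SAP does not say whether the Mann-Whitney test is applied to post-treatment values or to changes.

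**The concern.** Exercise therapy cannot alter a child's CP subtype, so a test of subtype by arm can only compare the arms at baseline. The same holds for medication if it was recorded at entry, which the SAP does not state. After random allocation the null hypothesis of such a test is true by design: a significant result is chance, and a non-significant one may only reflect a small sample.

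Subtype is therefore recorded, spent on a test that informs nothing, and left out of the analysis where it could help. If subtype predicts communication, daily-living or quality-of-life scores, two things follow. The unadjusted comparison carries avoidable noise. And if the arms happen to differ in subtype, the estimated difference is shifted, with nothing in the plan to take that out.

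**Working it through.** **Inputs.** From the documents: random allocation without stated stratification, the 5% level, chi-square for subtype, unadjusted Mann-Whitney for outcomes. The plan states no sample size, power, effect size or subtype distribution, so it has no figure to reproduce. Assumed: 1:1 allocation, two-sided tests, 20 per arm (range 10 to 50), subtype reduced to two classes at 50% each, normal scores with SD 1 within subtype, and a subtype shift g of 0.5, 1 or 1.5 SD. Normal scores are a simplification, since the SAP reports non-normal data.

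**1. What the chi-square can detect.** For 70% v 50% with n per arm, power = Φ[(0.20 − 1.96·√(2·0.6·0.4/n)) / √((0.7·0.3 + 0.5·0.5)/n)]. At n = 20 this is Φ[(0.20 − 0.304)/0.152] = Φ(−0.68) = 25%.

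| Per arm | 10 | 15 | 20 | 30 | 50 |
|---|---|---|---|---|---|
| Power, 70% v 50% | 14% | 20% | 25% | 35% | 53% |
| Largest difference with p ≥ 0.05 (points) | 40 | 33 | 30 | 23 | 18 |

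At 13/20 v 7/20, χ² = 40·(13·13 − 7·7)²/20⁴ = 3.6, p = 0.058. A 30-point difference is therefore not significant. Conversely, three independent tests under proper randomisation give at least one p < 0.05 with probability 1 − 0.95³ = 14%.

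**2. How often imbalance arises (exact binomial).** A difference of at least 20 points occurs in 27% of allocations at 20 per arm (50% at 10, 16% at 30). A difference of at least 30 points occurs in 8% at 20 per arm, and exactly 30 points in 4.2%.

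**3. Effect of a realised imbalance.** Shift = difference in proportion × g. For 12 v 8 and g = 1 it is 0.20 × 1 = 0.20 SD; for 13 v 7 it is 0.30 × 1 = 0.30 SD. Simulated false-positive rates at 20 per arm:

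| | g = 0.5 | g = 1 | g = 1.5 |
|---|---|---|---|
| Mann-Whitney, 12 v 8 | 5.4% | 5.7% | 6.2% |
| Mann-Whitney, 13 v 7 | 6.0–6.7% | 10.2–10.7% | 14.7–15.5% |
| Mann-Whitney, all allocations | 4.9% | 4.9% | 4.5% |
| Mann-Whitney, allocations with non-significant chi-square | 4.9% | 4.3% | 4.0% |

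A subtype-stratified rank test (van Elteren) stays at 4.9% to 6.1% on the 13 v 7 split.

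**4. Precision.** Ignoring a 50:50 subtype inflates the SD to √(1 + g²/4): 1.03, 1.12 and 1.25 for g = 0.5, 1 and 1.5. A 0.9 SD effect then acts like 0.9/1.03 = 0.87, 0.9/1.12 = 0.80 and 0.9/1.25 = 0.72. Simulated power at 20 per arm over all allocations:

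| | g = 0.5 | g = 1 | g = 1.5 |
|---|---|---|---|
| Mann-Whitney | 74.1% | about 67% | 58% |
| Stratified by subtype | 74.6% | about 76% | 75% |

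A rank regression on arm and subtype points the same way for a 0.8 SD effect. At g = 1, power rises from 57% to 66% (20 per arm) and from 75% to 84% (30 per arm). At g = 0.5 it rises only from 64% to 66% and from 82% to 84%.

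**5. Cost if subtype is not prognostic.** Van Elteren with three strata lowers power from 77% to 73% at 20 per arm, and from 47% to 39% at 10.

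**The case against.** The strongest reply is that the planned test is valid. Randomisation holds the Mann-Whitney error near 5% over all allocations, and no higher among allocations in which the chi-square is not significant. This stands. A reader might infer that the outcome comparison is biased, or that an error rate of about 11% applies in the 27% of trials with a 20-point imbalance. Neither follows. The higher rate belongs to the 13 v 7 split, and differences that large or larger arise in 8% of allocations. At 12 v 8 the rate is about 6%.

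Secondly, the chi-square is not the cause. The SAP does not call it a balance check, and deleting it changes no outcome result. This also stands: the substance is the missing adjustment.

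Thirdly, the gain rests on inputs that the documents lack. At a 0.5 SD subtype shift it is negligible. If the Mann-Whitney test is applied to changes, part of a stable subtype difference cancels.

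A reader might also infer that the medication-type test counts some children more than once, because the SAP lists the number of medications beside their types. The SAP does not describe the table layout. One category per child, or a yes/no per type, fits its wording equally well, so no breach of independence can be claimed.

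What the reply leaves untouched is that the p-values inform nothing, and that a factor already collected goes unused.

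**Conclusion.** The point holds as one of precision and reporting. The chi-square tests of subtype and medication by arm cannot show balance and serve no trial question, and the between-group outcome tests make no use of subtype.

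The size depends on assumptions. With 20 per arm, a two-class subtype at 50% and a 0.9 SD effect, the loss is about 9 points of power (67% v 76%) if subtype shifts scores by 1 SD, about 17 points (58% v 75%) at 1.5 SD, and about half a point at 0.5 SD. Distortion of the error rate is conditional on a marked realised imbalance; unconditionally the error is about 5%. The documents give no sample size, subtype frequencies or prognostic strength, so the true position within this range cannot be fixed from them.

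**What to change.** Replace the chi-square sentence in the SAP with wording to this effect: CP subtype and number and types of medication are shown by arm as n (%) without p-values. Each outcome scale is compared between arms with adjustment for CP subtype, merged into two classes before outcomes are examined, and for the baseline score where one was collected, using rank ANCOVA or an ordinal model. The adjustment is made whatever imbalance is seen. State also whether the comparison is of post-treatment values or of changes.

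If outcomes have already been analysed, keep the Mann-Whitney result as planned and report the adjusted comparison as a labelled sensitivity analysis.

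The cost is a change of wording and one adjusted model per scale, on data already collected. The downside is a small loss of power if subtype is not prognostic. That loss grows with many small strata, which is why two classes and a covariate model are preferable to fine stratification. Removing the p-values alone would tidy the report but change no outcome result.
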